Introduction: Glycemic control in acutely ill stroke patients with hyperglycemia is vital. Although insulin is the choice of anti-diabetic agent during acute stage, it is not clear which insulin regimen is better in terms of glycemic control and prevention of hypoglycemia in hospitalized acute stroke patients who are usually on small frequent nasogastric tube feeding. The present study aims to evaluate the efficacy and safety of human insulin (regular insulin and neutral protamine hagedorn, NPH insulin) to analog insulin (basal insulin glargine and rapid acting insulin aspart) in hospitalized acute stroke patients with hyperglycemia.

Justification: Analog insulins are developed by minor alteration of the amino acid chain which alters their pharmacokinetics and make them more physiological. However, these insulins are costly and are not widely available. Conventional human insulins are more commonly used in our country. Comparison of these two regimen is necessary in our own setting to optimize optimal glycemic management of hospitalized acute stroke patients.

Methodology: In this single-center, open-label, randomized trial, 100 patients with acute stroke and hyperglycemia (capillary blood glucose ≥ 10 mmol/L on 2 or more occasions) or history of type 2 DM admitted in the in-patient Department of Neurology, National Institute of Neurosciences (NINS) & Hospital will be randomly assigned to receive human insulin or modern insulin therapy in 1:1 ratio. The study will be carried out from February to June 2021. Blood glucose (BG) will be monitored by standardized glucometer thrice a day and insulin dose will be adjusted daily. The primary outcome of the study will be the differences in glycemic control between groups, as measured by mean daily BG concentration during the hospital stay. Secondary outcomes include differences between treatment groups in any of the following measures: number of hypoglycemic events (BG < 3.9 mmol/L), total daily dose of insulin, length of hospital stay, hospital complications and mortality.

Expected outcome/ result: The result will clearly show the efficacy and safety of newer insulins in comparison to conventional human insulin.

Recommendation: The study may help generating recommendations about insulin use in hospitalized acute stroke patients.

Section-C

INTRODUCTION:

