For a patient who is known to have diabetes but were not getting insulin previously (or previous insulin dosage is not known), insulin therapy will be started at a total daily dose of 0.3-0.4 units/kg/day for an admission BG between 10-15 mmol/L or 0.5-0.6 units/kg/day for a BG >15 mmol/L. In previously insulin treated patients, ongoing total daily dose of insulin will be started. If there is history of poor glycemic control with ongoing insulin dose, then 10-20% increase of daily dose of insulin will be considered.

For a patient who is not known to have diabetes, insulin therapy will be started if admission BG is >10 mmol/L in two or more occasions. A total daily dose of 0.3-0.4 units/kg/day will be started if admission BG is 10-15 mmol/L and 0.5-0.6 units/kg/day for a BG >15 mmol/L.

Patients treated with human insulin regimen will receive 50% of total daily dose as NPH insulin at around 6 am and 6 pm, while the rest 50% regular human insulin three times a day in 3 equally divided doses at around 6 am, 12 pm and 6 pm.

Patients treated with modern insulin regimen will receive 50% of total daily dose as basal insulin glargine at the same time of day and 50% as insulin aspart given in 3 equally divided doses at 6 am, 12 pm and 6 pm.

In both groups, insulin dosage will be adjusted daily to a target fasting and premeal BG 7.8-10.0 mmol/L in the absence of hypoglycemia. Insulin dosage will be adjusted daily according to BG values. If the fasting and/or premeal BG is 10-15 mmol/L in the absence of hypoglycemia, the total daily dose will be increased by 10% every day. If the fasting and/or premeal BG is >15 mmol/L, the insulin daily dose will be increased by 20% every day. If a patient develops hypoglycemia (BG <3.9 mmol/L), the insulin daily dose will be decreased by 20%. Supplemental regular insulin will be given in addition to scheduled mealtime insulin for BG >10 mmol/L using a supplemental insulin protocol.

BG will be measured before each bolus insulin injection (at 6 am, 12 pm and 6 pm). Glycated hemoglobin (HbA1c) will be measured after hospital admission if not done within last three months.

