Except anti-diabetic treatment, other treatments will be continued as per the decisions of the treating physicians. If NG feeding is discontinued and patient is kept NPO, conventional group will receive neutralizing insulin with any dextrose containing fluid along with low dose NPH insulin, if needed. Modern insulin group will receive neutralizing insulin with any dextrose containing fluid with glargine insulin as before.

After recruitment, each recruited patient will be visited daily (even in holidays according to a predefined schedule) by one of the investigators and insulin dose will be adjusted according to glucose profile of previous day. Insulin injection and capillary blood glucose monitoring by glucometer will be done by trained nurses as part of their routine patient care. Doctors and nurses on duty will be provided with cell number of the investigators who will receive call on 24/7 basis for any emergency or uncertainty regarding management of hyperglycemia.

Hypoglycemia is regarded as the only short-term adverse event of insulin. As both treatment arms will use established and recognized insulin regimen, no compensation will be provided to the patient or his/her attendants in case of any adverse event. As most of the hospitalized patients have severe stroke with case fatality rate around 20%, death will not be regarded as parameter of primary treatment outcome.

During discharge, last in-hospital insulin dose will be continued with education to the caregiver regarding insulin injection and glucose monitoring technique. No follow up visit is included in the study.

Protocol deviation and protocol violation:

Deviation to protocol will be recorded and reported to ethical committee as soon as possible. Failure to obtain informed written consent, use of incorrect insulin regimen, not fulfilling inclusion and exclusion criteria will be regarded as protocol violation and will be reported to ethical committee immediately. In case of protocol violation, the data of related participant will be discarded.

Outcome variables

The primary efficacy outcome of the study will be the differences in glycemetic control between groups, as measured by mean daily BG concentration during the hospital stay.

The primary safety outcome will be the frequency of hypoglycemic events (BG <3.9 mmol/L).

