Secondary outcomes include differences between treatment groups in any of the following measures: total daily dose of insulin, length of hospital stay, hospital complications, and mortality.

Data collection technique

Data will be collected in a predesigned questionnaire by the research team. The researchers will recheck randomly and blindly to verify the collected data.

Data management

All data will be compiled and edited meticulously by thorough checking and rechecking. All omissions and inconsistencies will be corrected and will be removed methodically.

Statistical analysis

Computer based statistical analysis will be carried out with appropriate techniques and systems by SPSS 22.0. Quantitative data will be expressed as mean and standard deviation or median and inter-quartile range; and qualitative data will be expressed as frequency and percentage. Continuous variables, analysis will be made by the Students T-test or Mann-Whitney *U* test. Categorical variables will be analyzed by the χ^2 test. All probabilities will be 2-tailed. Statistical significance will be accepted at $p \leq 0.05$.

Utilization of results

The result of study will be helpful for the physicians to choose appropriate insulin regimen in patients hospitalized with acute stroke having hyperglycemia. It will also help the policy makers in ensuring adequate supply of appropriate insulin that may help improve the outcome of patients.

FLOW CHART

Sl. No.	Job Title	Feb'21	Mar'21	Apr'21	May'21	Jun'21
1.	Questionnaire Validation	√				
2.	Data Collection	√	√	√		
3.	Data Analysis				√	
4.	Report writing and Printing				√	√
5.	Submission					√

ETHICAL IMPLICATIONS:

Prior to the commencement of this study, approval of the institutional review board (IRB) of National Institute of Neurosciences & Hospital, Dhaka will be sought. The aims and objectives of the study along with its procedure, risks and benefits of this study will be explained to the patients or attendants of the patients in easily understandable local language and then written consent will be taken from each. It will be assured that all information and records would be kept confidential.

Role of funding agency

The funding agency will have no role in protocol development, data collection, analysis, interpretation or writing the report. The authors will have full access to all study data and will have the final responsibility for the decision to submit for publication.

REFERENCES:

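### Does the plan need a stated counting unit for hypoglycaemic events, and a rule for deaths in length of stay?

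*Combined protocol and SAP*

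**What the plan says.** Section-C, Methodology, Outcome variables: "The primary safety outcome will be the frequency of hypoglycemic events (BG <3.9 mmol/L". The summary before Section-C and the Abstract for IRB/Ethical Committee both place the "number of hypoglycemic events (BG < 3.9 mmol/L" among the secondary outcomes.

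Section-C, Statistical analysis, says "qualitative data will be expressed as frequency and percentage" and "Continuous variables, analysis will be made by the Students T-test or Mann-Whitney" U test. Categorical variables go to χ². All tests are two-sided at 0.05. Hypoglycaemia is not assigned to either class of variable.

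Study Procedure sets three glucose readings a day and adds "Insulin dosage will be adjusted daily according to BG values". Observation stops when the patient leaves hospital: "No follow up visit is included in the study". On deaths it gives a "case fatality rate around 20%, death will not be regarded as parameter of primary treatment outcome". The secondary outcomes in Section-C are "total daily dose of insulin, length of hospital stay, hospital complications, and mortality", with no rule linking the last of these to length of stay.

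**The concern.** The primary safety outcome carries a glucose threshold but no unit. *Frequency* in Outcome variables could mean patients with an event, since Statistical analysis uses that word for qualitative data; *number* in the two abstracts points to a count. The outcome is also primary in one place and secondary in two. In an open-label trial, a unit left open could be chosen after the results are seen, and the choice affects power.

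Time observed differs between patients. If one arm stays longer, it collects more events at the same daily risk, and a count or an ever/never comparison would show a difference. For length of stay, an early death kept as raw days looks like a short admission, so an arm with more deaths could seem to do better. At a case fatality of about 20%, roughly 0.20 × 50 = 10 patients per arm are affected.

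**Working it through.** **The plan's own figure.** The only computed figure is the sample size for glucose: 2 × ((1.645 + 0.845)/3)² × 6² = 49.6, so 50 per group. (The list above that line gives 8 rather than 6; that is a separate matter.) Nothing is computed for hypoglycaemia or length of stay. The documents give no event rate, length of stay or day of death, so everything below rests on assumed values.

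**Setting.** 50 per arm, two-sided 0.05, gamma-distributed stays, events varying between patients, 1,500-3,000 simulated trials per setting.

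**1. Same daily risk in both arms: false rejection**

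| Assumed mean stay | Analysis | Rejection |
|---|---|---|
| Equal | χ² on patients, Mann-Whitney or t-test on counts | 4-6% |
| 9 vs 10 days | χ², Mann-Whitney | 5.6-8% |
| 8 vs 11 days | χ², Mann-Whitney on counts | 7-21% |
| 8 vs 11 days | negative binomial, patient-days offset | 4.6-6.4% |
| 8 vs 11 days | t-test on each patient's events per day | 4.0-4.8% |
| 8 vs 11 days | Mann-Whitney on events per day | 7.6-10.1% |

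At 0.1 events per day, 8 vs 11 days means 0.1 × 8 = 0.8 against 0.1 × 11 = 1.1 events per patient. That is a true difference per admission; it is false only as a statement about daily risk. Unequal deaths alone do little: 5.7-6.3% at 20% vs 30% mortality with deaths near day 4, and 8.3-8.5% at 10% vs 30% near day 3.

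**2. Do the listed tests ignore time observed?** No. Events per day is a continuous variable for each patient, so the planned t-test applies to it. It holds its size in the table above.

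**3. Power for a true doubling of the daily rate, equal 10-day stays**

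| Analysis | Power |
|---|---|
| χ² on patients with an event | 37% |
| Mann-Whitney on counts | 54% |
| Mann-Whitney on events per day | 59% |
| t-test on events per day | 67-69% |
| Negative binomial with offset | 71% |

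The extra model gains 2 to 4 percentage points over a test already in the plan.

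**4. Risk concentrated early.** Doses are titrated daily, so constant risk cannot be assumed. With risk only in the first 5 days, equal between arms, and stays of 8 vs 11 days: χ² 6.4-7.8%, Mann-Whitney on counts 6.3-7.5%, offset model 10.4-15.4%. Under early risk the t-test on events per day shares the weakness (9.0-12.2%). Dividing by days corrects one error and adds another.

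**5. Length of stay.** Assume survivors stay 10 days and deaths occur at day 4.

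- 20% mortality: 0.8 × 10 + 0.2 × 4 = 8.8 days.
- 30% mortality: 0.7 × 10 + 0.3 × 4 = 8.2 days.

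The raw-days comparison then rejects in 6.1-9.8% of trials. At equal 20% mortality it rejects in 4.3-5.2%. With deaths at day 15 the means are 0.8 × 10 + 0.2 × 15 = 11.0 and 0.7 × 10 + 0.3 × 15 = 11.5, so the direction reverses, and rejection is near nominal (5.9%).

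**The case for a change.** The strongest case for a change is that this is the primary safety outcome of an open-label trial, and that the permitted units differ in power from 37% to about 70% even when stays are equal. A sentence fixing the unit would cost almost nothing. That stands as a remark on drafting. It does not show that the planned analysis is invalid: each patient-level reading keeps its size when stays are equal.

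A second argument is that χ² on individual readings, not excluded by the text, rejects falsely in 16.5-23.9% of trials with equal stays if patients differ strongly in risk (assumed rate variance 2 or 4 around a mean of 1). The arithmetic is right. But it treats repeated readings on one patient as independent, which the text does not ask for and a competent analyst would not do.

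A third is that reporting mortality beside length of stay protects little. For 20% vs 30% with 50 per arm, the standard error is √(2 × 0.25 × 0.75/50) = 0.087, so z = 0.10/0.087 = 1.15 and power is about 21%. This is true of the test. A reader still sees the deaths by arm next to the days, which is what is needed to recognise a short stay caused by early death.

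The fuller alternative is a rate model with a first-event or early-window check, and time to discharge alive. It would leave several hypoglycaemia analyses with none named as deciding, and would still lack a rule for when two low readings are one event. It does not settle the unit.

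**Conclusion.** No change follows. The missing unit, denominator and death rule are gaps that analysts fill sensibly with what the plan already provides: patients with at least one event by χ², events per patient-day by t-test, and length of stay read beside deaths. The primary outcome, mean daily glucose over the stay, already requires readings by day, so low readings and days observed should come from the same data. The primary/secondary mismatch is a labelling slip: it alters no test, significance level or sample size.

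The size is small in the settings the documents support: 4-6% false rejection with equal stays, and 4.3-5.2% for length of stay at equal mortality. The larger figures depend on an assumed gap of about 3 days between randomised arms, or on early and unequal deaths. A rate model is a fair trade-off and not a clear gain, because it does worse than the plan's tests on patients or counts when risk is early. If the arms do turn out to differ clearly in stay or mortality, the event counts and days should be read with that in view.

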In different countries, basal-bolus therapies with insulin analogs are being used more commonly. But intermediate-acting and regular human insulin are also observed to have almost similar efficacy and safety (12,14). No inpatient trials have been conducted in our region to determine optimal treatment regimens for hospitalized patients with T2DM in special situation like acute stroke. As there are significant differences in patient demographics, admission cause, feeding practice and availability of hospital resources between patients of developed and developing countries, the choice of agents may not be similar (15,16). In this background, the present study aims to compare the efficacy and safety of conventional human insulin (regular insulin and intermediate acting NPH insulin) to newer analog insulin (basal insulin glargine with rapid acting insulin aspart) in acute stroke patients with hyperglycemia admitted in a referral tertiary neuroscience institute of Dhaka.

RATIONALE:

One in five patients hospitalized for acute stroke has hyperglycemia. For optimum outcome of these patients, proper glycemic control is essential. Acute stroke patients, who need hospitalization, are usually unable to take food normally and they are fed through nasogastric tube with small frequent feeding (200 ml, 2-hourly, 10 feed/day). It is not clear which insulin regimen will suit better to these type of feeding practice. Moreover, corticosteroids (dexamethasone) are often used in these patients as treatment adjunct which further challenges glucose homeostasis. Different insulin regimens are used in such patients but none is validated in clinical trials. Episodes of hypoglycemia may cause further neurological deterioration in acute stroke patients. So regimen with less chance of hypoglycemia needs to be identified. Although analog insulins are observed to have less chance of hypoglycemia, they are costly and had not been well studied in our setting. It is essential for us to know the efficacy and safety of analog insulin regimen in comparison to human insulin, so that appropriate management decision can be made

OBJECTIVES:

General objective:

- To compare the efficacy and safety of human insulin (regular insulin and intermediate acting NPH insulin) to analog insulin (basal insulin glargine and rapid acting insulin aspart) in hospitalized acute stroke patients with hyperglycemia

Specific objectives:

In hospitalized acute stroke patients with hyperglycemia -

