- To evaluate the efficacy and safety of human insulin (regular insulin and intermediate acting NPH insulin)
- To assess the efficacy and safety of insulin analog (basal insulin glargine and rapid acting insulin aspart)
- To compare the efficacy and safety of two insulin regimen
- To evaluate the socio-demographic and clinical characteristics of the patients included in two treatment arms

METHODOLOGY:

Type of study: Single-center, open-label, randomized trial

Place of Study: Department of Neurology, National Institute of Neurosciences & Hospital, Dhaka.

Study Period: February to June, 2021

Study population: Patients admitted in the Department of Neurology with acute stroke and hyperglycemia

Sample Size:

Sample size was calculated according to following formula for non-inferiority trial (17):

$$N = 2 \times \left(\frac{Z_{1-\alpha} + Z_{1-\beta}}{\delta_0} \right)^2 \times S^2$$

Here, N= sample size per group

$$\alpha = 0.05$$

$$\beta = 0.20$$

δ_0 = a clinically acceptable margin (assumed as 3 mmol/L of blood glucose)

S² = Pooled standard deviation of both comparison group = 8

So,

$$N_{\text{non-inferiority}} = 2 \times \left(\frac{1.645 + 0.845}{3} \right)^2 \times 6^2 = 50$$

As a result, 50 patients will be randomly assigned to two treatment groups (50 human insulin regimen, 50 analog insulin regimen).

Inclusion criteria

- Patients admitted to adult neurology ward with acute stroke with
- Patients having hyperglycemia (capillary blood glucose ≥ 10 mmol/L in 2 or more occasions or having history of treatment for DM)
- Patients with age of 18-80 years of both sexes
- Patients or their attendants giving consent to take part in the study

Exclusion Criteria

- Patients with hyperglycemic emergencies (hyperglycemic hyperosmolar state or diabetic ketoacidosis)
- Pregnant patients
- Those not giving consent to participate in the study

Study Procedure

Patients will be randomly assigned to receive either a human insulin regimen (starting with regular insulin three times a day with NPH insulin twice a day) or analog insulin regimen (basal insulin glargine once daily and insulin aspart three times a day) following a computer-generated randomization table. All oral antidiabetic drugs will be discontinued on admission.

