Abstract for IRB/Ethical Committee:

Glycemic control in acutely ill stroke patients with hyperglycemia is vital. Although insulin is the choice of anti-diabetic agent during acute stage, it is not clear which insulin regimen is better in terms of glycemic control and prevention of hypoglycemia in hospitalized acute stroke patients who are usually on small frequent nasogastric tube feeding. The present study aims to evaluate the efficacy and safety of human insulin (regular insulin and neutral protamine hagedorn, NPH insulin) to analog insulin (basal insulin glargine and rapid acting insulin aspart) in hospitalized acute stroke patients with hyperglycemia. In this single-center, open-label, randomized trial, 100 patients with acute stroke and hyperglycemia (capillary blood glucose ≥ 10 mmol/L on 2 or more occasions) or history of type 2 DM admitted in the in-patient Department of Neurology, National Institute of Neurosciences (NINS) & Hospital will be randomly assigned to receive human insulin or modern insulin therapy in 1:1 ratio. The study will be carried out from February to June 2021. Blood glucose (BG) will be monitored by standardized glucometer thrice a day and insulin dose will be adjusted daily. The primary outcome of the study will be the differences in glycemic control between groups, as measured by mean daily BG concentration during the hospital stay. Secondary outcomes include differences between treatment groups in any of the following measures: number of hypoglycemic events (BG < 3.9 mmol/L), total daily dose of insulin, length of hospital stay, hospital complications and mortality. Computer based statistical analysis will be carried out by SPSS 22.0. Quantitative data will be expressed as mean and standard deviation or median and inter-quartile range; and qualitative data will be expressed as frequency and percentage. Continuous variables will be compared by the Students T-test or Mann-Whitney *U* test. Categorical variables will be analyzed by the χ^2 test. All probabilities will be 2-tailed. Statistical significance will be accepted at $P \leq 0.05$. Prior to the commencement of this study, approval of the institutional review board (IRB) of NINS will be sought. The aims and objectives of the study along with its procedure, risks and benefits of this study will be explained to the patients or attendants of the patients in easily understandable local language and then written consent will be taken from each. The result of the study may help us to choose appropriate insulin regimen for hospitalized acute stroke patients in our setting.

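### The trial is sized for non-inferiority with a 3 mmol/L margin, but the planned analysis has no margin rule, confidence-interval rule or named reference regimen, so the 80% power does not belong to it

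*Combined protocol and SAP*

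**What the plan says.** In the combined protocol and SAP, the Sample Size section under METHODOLOGY states: "Sample size was calculated according to following formula for non-inferiority trial". The margin is "a clinically acceptable margin (assumed as 3 mmol/L of blood glucose", with α = 0.05, β = 0.20 and normal quantiles 1.645 and 0.845. The SD is defined as "Pooled standard deviation of both comparison group = 8", but the worked line uses 6 and arrives at 50 per group.

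The margin and the term non-inferiority appear nowhere else in the plan. The summary at the front says: "The primary outcome of the study will be the differences in glycemic control between groups, as measured by mean daily BG concentration". The Outcome variables section agrees: "The primary efficacy outcome of the study will be the differences in glycemetic control between groups". So does the Abstract for IRB/Ethical Committee: "The primary outcome of the study will be the differences in glycemic control between groups". None of these gives a direction or a margin.

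For the analysis, the Statistical analysis section says: "Continuous variables, analysis will be made by the Students T-test or Mann-Whitney" U test, with all probabilities two-tailed and significance at p ≤ 0.05. The IRB abstract repeats this. Neither mentions a confidence interval.

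The General objective is "To compare the efficacy and safety of human insulin (regular insulin and intermediate acting NPH insulin) to analog insulin". The Expected outcome paragraph and the RATIONALE put the regimens in the opposite order. None of them designates a reference regimen.

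**The concern.** A non-inferiority test asks whether the test regimen's mean glucose exceeds the reference regimen's by less than the margin. It needs three things fixed in advance: the margin, the direction (which arm is test and which is reference) and the confidence level. The sample size section supplies the margin and the one-sided level. The analysis section carries neither forward, and the direction is given nowhere.

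Followed as written, the plan never runs the test on which its 50 per arm is based. It states no power for the test it does describe. No rule says how a non-significant primary result is to be read.

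This matters for use of the result. The Utilization of results section intends the findings to guide physicians' choice of regimen and policy makers' supply decisions, and the Justification stresses the cost of analog insulin. A p-value above 0.05 could easily be reported as showing that the two regimens are equally good, which it does not show. If the margin rule is instead added after the results are known, the confidence level and the direction can be chosen to suit them.

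**Working it through.** **Inputs (Sample Size section).** Margin δ₀ = 3 mmol/L; quantiles 1.645 and 0.845; SD 6 in the worked line and 8 in the definition; n = 50 per arm. From the Statistical analysis section: two-tailed, p ≤ 0.05.

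**1. The plan's own figure.** N = 2 × ((1.645 + 0.845)/3)² × 6² = 49.6, rounded up to 50 per arm. This is reproduced. With one-sided 5%, SD 8 would give 88 per arm, and reading 8 as a variance would give 11. Only SD 6 gives 50, so SD 6 leads below and SD 8 is shown beside it.

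**2. Standard error of the difference.** SE = SD × √(2/50), which is 1.20 at SD 6 and 1.60 at SD 8.

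**3. Power of the test used for sizing.** For true difference 0, power = Φ(3/SE − z).

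| Interval | z | SD 6 | SD 8 |
|---|---|---|---|
| 90% two-sided (one-sided 5%) | 1.645 | 80.4% | 59.1% |
| 95% two-sided (one-sided 2.5%) | 1.960 | 70.5% | 46.6% |

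The noncentral t distribution gives 79.9% and 58.6% for the first row, and 69.7% and 45.9% for the second.

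**4. Power of the test as planned.** This takes the null to be zero difference, two-tailed 5%. At true difference 0, the assumption behind N, it rejects 5% of the time. At a true 3 mmol/L its power is 69.7% (SD 6) or 45.9% (SD 8) by noncentral t. It reaches 80% only at a true difference of 3.40 mmol/L (SD 6) or 4.53 mmol/L (SD 8).

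**5. Where the two rules part.** Let d be the observed mean BG in the test arm minus that in the reference arm, using the normal approximation.

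- Non-inferiority on a 90% interval fails if d > 3 − 1.645 × SE: 1.03 at SD 6, 0.37 at SD 8.
- The difference is non-significant if |d| < 1.96 × SE: 2.35 at SD 6, 3.14 at SD 8.

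An observed excess of 1.03 to 2.35 mmol/L (SD 6), or 0.37 to 3.14 mmol/L (SD 8), is therefore non-significant yet fails non-inferiority.

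**6. How often this happens when the regimens are truly equal.**

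- Non-significant and non-inferiority fails: 0.975 − 0.804 = 0.171 at SD 6; 0.975 − 0.591 = 0.384 at SD 8. Simulation with estimated SDs and t critical values gives 0.176 and 0.389.
- Non-significant and non-inferiority met: 0.804 − 0.025 = 0.779 at SD 6; 0.591 − 0.025 = 0.566 at SD 8.

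The p-value alone does not separate these two groups of trials.

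**7. Variance reading.** If 8 were a variance (SD 2.83, SE 0.566), the rules would part the other way: an excess between 1.96 × 0.566 = 1.11 and 3 − 1.645 × 0.566 = 2.07 mmol/L would be significant yet meet non-inferiority. That is a coherent outcome, but it too needs a stated rule.

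**The case against.** The strongest reply is that nothing is lost. The data are the same under either framework, standard t-test output includes a confidence interval for the difference, and that interval can be compared with 3 mmol/L at any time. The plan also never states a null of zero, so the difference test is the reader's inference. If the regimens are equal and the SD is 6, about 78% of trials would be both non-significant and non-inferior on a 90% interval, so the usual conclusion would be right.

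Much of this is true. The data stay valid, the null of zero is an inference, and a non-significant result is inadequate only when the p-value is used by itself. But a two-tailed p ≤ 0.05 with no margin has no other natural reading, and the omitted rule is what decides the remaining cases. The choice of a 90% or 95% interval alone moves power from about 80% to about 70% at SD 6.

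On the reference regimen, it can be said that comparing one thing to another is symmetric, and that the RATIONALE and the remark that human insulin is more commonly used locally lean towards human insulin as reference. That is fair: the differing word order is not itself a contradiction. The reference is still not named, and a one-directional hypothesis cannot be written without it.

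**Conclusion.** The concern holds. The sample size rests on a non-inferiority test that the analysis plan does not contain, and the plan gives no power for the two-tailed test it does contain. The defect is an undefined decision rule for the primary comparison. It does not invalidate the data or the choice of a t-test.

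At SD 6, the planned test has about 70% power for a true 3 mmol/L difference, and about 17% of trials of equal regimens would be non-significant yet fail the margin. At SD 8 these figures are about 46% and 38%.

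The figures assume 50 analysed patients per arm, the t-test rather than the rank test, higher glucose counted as worse, and, for non-inferiority power, a true difference of 0. The mismatch exists at either SD. The conflict between 6 and 8, the rule on discarding violators' data and the basis for the margin are separate points.

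**What to change.** Choose one framework and write it into the Statistical analysis section before recruitment. Failing that, do so before any between-arm summary or comparison is produced, and record the date. The trial is open-label and investigators see each patient's glucose readings daily, so a condition that nobody has seen outcome data could not be met once patients are enrolled.

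**(a) Keep non-inferiority.** Name the test and reference regimens. Declare non-inferiority if the upper limit of the two-sided 90% confidence interval for mean BG (test minus reference) is below 3 mmol/L. State the power, at true difference 0 and 50 analysed per arm, as about 80% at SD 6 and 59% at SD 8. If a 95% interval is preferred, restate it as about 70% and 46% to 47%. If a rank method is used, compare the Hodges-Lehmann interval with the margin.

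**(b) Keep the two-tailed difference test.** Remove the non-inferiority basis from the Sample Size section. State that 50 per arm gives about 70% power for a 3 mmol/L difference at SD 6 (46% at SD 8), and 80% power for about 3.4 mmol/L (4.5 at SD 8).

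Either way, add that p > 0.05 will not be read as equivalence or non-inferiority.

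**Cost.** Option (a) with a 90% interval changes wording only. Option (a) with a 95% interval, or option (b), means stating a less favourable power. No patients are added.
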